## **APPENDIX 1: ANNOUNCEMENT TEXT**

We are looking for volunteer residents who were previously assigned to ICU during Covid-19 pandemic, for a mannequin study titled "Assessment of Cardiopulmonary Resuscitation Skills with Simulation in ICU". Those who want to participate in the study can apply to [name] [name].

## **APPENDIX 2: DATA COLLECTION FORM**

1. Participant Number:
1. Group: Experiment/Control
2. Age:
3. Gender:
4. Medical Branch:
5. Years of residency:
6. Number of CPR experiences:
7. Number of CPRs performed during Covid-19 ICU
8. Working time in Covid-19 ICU
9. Do you have a basic life support training certificate after graduation? Yes/No

## **APPENDIX 3: INTERVIEW QUESTIONS**

1. What is your profession/duty?
2. How long and how often did you work in the intensive care unit during the pandemic?
3. What can you say about your experiences while working in the intensive care unit during the pandemic?
4. Were there any facilitating factors/comforting factors for you in this process? If so, what were these factors?
5. Were there any factors that made it difficult for you / hindered your work / disturbed you during this process? If so, what were these factors?
6. What are your thoughts on doctors who do not have intensive care experience employing in intensive care units in cases such as pandemics/epidemics/disasters?
7. In this pandemic, intensivists and non-intensivist doctors worked together. What would you say about this experience?
8. Intensivist doctors can work in intensive care unit with non-intensivist doctors in cases such as pandemics/epidemics/disasters, as in the current period. What needs to be done in order for this process to be carried out in a correct way?
9. Do you think there is a difference between you and an intensivist doctor in terms of success and effectiveness in basic life support and CPR?

## **APPENDIX 4: CPR EVALUATION FORM**

Please rate participants' CPR performance from 1 to 4 based on the questions below.

1. Are the chest compressions applied to the correct place?
  1. Completely wrong place (ex: abdomen)
  2. Correct place - less than 50% of the time
  3. Correct place - more than 50% of the time
  4. Correct place
2. Are the hands placed correctly?
  1. Hands/elbows completely wrong (eg: hands made into fists, elbows bent)
  2. Hand position correct (but wrong angle or hands are not clasped)

3. Too close to the correct position and angle (the heel of the hand is in full contact and does not separate)
  4. Completely in the correct position/angle and does not distort
3. Is effective compression applied?
    - 1- Effective in less than 25% of the time
    - 2- Effective in 25-50% of the time
    - 3- Effective in 50-75% of the time
    - 4- Effective in more than 75% of the time
  4. Is appropriate compression number per minute applied?
    1. Too fast or too slow
    2. In correct range less than 50% of the time
    3. In correct range more than 50% of the time
    4. In correct range all the time
  5. Is 30:2 compression/ventilation synchronization applied?
    - 1- Completely wrong
    - 2- 15/2
    - 3- Only compression/ or later 30/2
    - 4- Completely correct
  6. Is the compression depth appropriate?
    1. Too deep or too superficial
    2. At the appropriate depth less than 50% of the time
    3. At the appropriate depth more than 50% of the time
    4. At the appropriate depth
  7. Is the rib cage allowed to retract?
    - 1- Not allowed
    - 2- Allowed more than 50% of the time
    - 3- Allowed more than 50% of the time
    - 4- Allowed
  8. Is he/she able to continue chest compressions without a break) (No more than 5 seconds)
    - 1- He/she took a break for more than 5 seconds (out-of-guide application: 15/2 or 2/15)
    - 2- He/she took a break for more than 5 seconds (while 30/2)
    - 3- He/she didn't take a break (just compression)
    - 4- He/she took a break for less than 5 seconds (while 30/2)
  9. Did he/she perform effective mask ventilation?
    - 1- Did not perform mask ventilation
    - 2- Performed mask ventilation carelessly
    - 3- Performed mask ventilation but failed
    - 4- Completely correct one-hand mask ventilation/bedside position

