### ***Part Two: Mannequin Study***

In the second part, both the intensivist and the non-intensivist groups will be randomly divided into two subgroups as experiment and control. Then, stereotype threat manipulation will be performed on experimental group just before they are taken into the testing room. For manipulation, the following sentences will be said: “Studies have shown that intensive care workers are more successful in CPR. In this study, we aim to compare the CPR performance between ICU and other branches.”. The other group (Control Group) will not be given any prior information.

All participants will play a standard CPR simulation scenario under the supervision of an intensivist physician who is blind to the groups. Participants' performance will be measured with a CPR simulator mannequin (Resusci Anne Simulator®, 'Laerdal Medical'). All performants will be videotaped during simulation. Later, these videotapes will be evaluated and scored separately by three independent resuscitation instructor anesthesiologists who are blinded to groups (Appendix 4: CPR Evaluation Form). The total simulation score will be obtained by adding the objective scores obtained from the simulator's data (Appendix 5: Mannequin Scores) to the average subjective scores of the independent resuscitation instructors.

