## **APPENDIX 5: MANNEQUIN SCORES**

Scores of cardiopulmonary resuscitation simulator mannequin (Resusci Anne Simulator®, 'Laerdal Medical').

1. Chest compression number per minute (n: 100-120)
  1. Too fast or too slow
  2. In correct range less than 50% of the time
  3. In correct range more than 50% of the time
  4. In correct range all the time
  
2. Chest compression depth (n: 5-6 cm)
  1. Too deep or too superficial
  2. At the appropriate depth less than 50% of the time
  3. At the appropriate depth more than 50% of the time
  4. At the appropriate depth
  
3. Are the chest compressions applied to the correct place?
  1. Completely wrong place (ex: abdomen)
  2. Correct place - less than 50% of the time
  3. Correct place - more than 50% of the time
  4. Completely correct place

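### Item 7 of the CPR evaluation form (chest recoil) gives codes 2 and 3 the same wording, a minor scoring error in one component of the dependent variable

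*Combined protocol and SAP*

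**What the plan says.** Appendix 4, item 7, asks whether the rib cage is allowed to retract. Code 1 is recoil not allowed and code 4 is recoil allowed. Between them, code 2 is printed as "2- Allowed more than 50% of the time" and code 3 as "3- Allowed more than 50% of the time".

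Other items on the same 1-to-4 scale keep codes 2 and 3 apart. In Appendix 4, item 1, code 2 is "Correct place - less than 50% of the time" and code 3 is the matching more-than-half wording; items 4 and 6 follow the same pattern. So do all three simulator items in Appendix 5, for example code 2 for depth: "At the appropriate depth less than 50% of the time". Appendix 4, item 3, uses bands that also meet at 50%: "2- Effective in 25-50% of the time" and "3- Effective in 50-75% of the time".

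The section Part Two: Mannequin Study says of the recordings that "these videotapes will be evaluated and scored separately by three independent resuscitation instructor anesthesiologists who are blinded to groups". The raters' average is added to the simulator score to give the total simulation score. The section Analysis of data makes the simulation score the dependent variable.

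**The concern.** The four codes of item 7 carry only three distinct descriptions. A performance with recoil for more than half but not all of the time matches codes 2 and 3 equally. One with some recoil, but for no more than half of the time, matches no code, and the rater must choose between 1, 2 and 3 without guidance. Only absent and full recoil can be scored as the form stands.

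The three raters work separately, and neither the form nor the protocol ensures that they resolve this in the same way. The likely results are some noise, less discrimination among partial-recoil performers and lower rater agreement on this item. Appendix 5 covers compression rate, depth and place but not recoil, so no simulator measurement offsets the error.

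A shift between groups is also possible. Raters blinded to group cannot favour one, but if partial recoil is more frequent in one group, a consistent misreading moves that group's mean further than the other's.

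**Working it through.** The documents give no score range, standard deviation (SD), sample size or power for the mannequin study, so there is no planned figure to reproduce. The check has two parts: a comparison of the wording, and a bound on the effect.

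**Wording of codes 2 and 3**

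| Item | Code 2 | Code 3 |
|---|---|---|
| Appendix 4, items 1, 4, 6 | below 50% | above 50% |
| Appendix 5, items 1, 2, 3 | below 50% | above 50% |
| Appendix 4, item 3 | 25 to 50% | 50 to 75% |
| Appendix 4, item 7 | above 50% | above 50% |

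Item 7 is the only one of these eight that does not separate the two codes. Both of its lines are complete and separately numbered, so a text-extraction fault is not a plausible explanation.

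**Score range.** Inputs: nine rater items (Appendix 4) and three simulator items (Appendix 5), each coded 1 to 4, and three raters whose scores are averaged. The plan does not say how items combine within a form; summing is assumed.

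- Rater form: 9 × (4 − 1) = 27 points
- Simulator: 3 × (4 − 1) = 9 points
- Total: 27 + 9 = 36 points, of which item 7 carries 3 (3/36 = 8.3%)

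**Largest shift for one participant.** An intended 2 can become 1 or 3, and an intended 3 can become 2, so each rater can be off by at most 1 point.

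- All three raters off: 1 point; 1/36 = 2.8% of the range
- One rater off: 1/3 = 0.33 points; 0.33/36 = 0.9%
- If the nine rater items are averaged instead: 1/9 = 0.11 points. The range shrinks too: 3 + 9 = 12 with simulator items summed (0.11/12 = 0.9%), or 3 + 3 = 6 with both averaged (0.11/6 = 1.9%)

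**Shift between groups under one consistent misreading.** Bound = 1 point × difference between groups in the share of affected performances. The differences below are assumed.

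- 10 percentage points: 1 × 0.10 = 0.1 points (0.3% of 36)
- 30 percentage points: 1 × 0.30 = 0.3 points (0.8% of 36)
- Equal shares: zero

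**Noise if raters guess case by case.** A 50:50 choice between 2 and 3 has variance 0.25. For the three-rater mean on an affected performance:

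- Independent choices: 0.25/3 = 0.083 (SD 0.29)
- Fully shared choice: 0.25 (SD 0.50)

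To put this on the scale of the total score, let q be the share of participants affected and v the added variance. The SD then inflates by the factor √(1 + q·v/SD²). For an assumed total-score SD of 3 to 6 points and q from 25% to 100%:

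- Independent choices: inflation of 0.03% to 0.46%
- Fully shared choices: inflation of 0.09% to 1.4%

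In the worst case (q = 1, v = 0.25, SD = 3), √(1 + 0.25/9) = 1.014. Taking alpha of 0.05 as two-sided, which the plan does not state, a nominal 80% power becomes Φ((1.960 + 0.842)/1.014 − 1.960) = 78.9%.

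If each rater instead keeps to one reading throughout, the result is a fixed offset on affected performances and not random noise.

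**The case against.** The strongest reply is that the slip corrects itself. The codes are ordered, the two endpoints are clear, items on the same form show the pattern, and the raters are resuscitation instructors. They will probably read code 2 as less than half. The documents also do not show that this English text is the form the raters will hold. This limits the likely harm, but it does not ensure that three people scoring separately agree.

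On the shift between groups, the reply is largely right for experiment against control. That split is randomised within each specialty group, so if the stereotype-threat message has no effect, the expected shares of partial recoil are equal and a consistent misreading creates no spurious difference; it can only distort a real one. The comparison of intensivists with non-intensivists is not randomised, and unequal shares can arise there without any effect of the message. The assumed 10 to 30 percentage points have no basis in the documents.

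It is also fair that the noise costs almost nothing in power, and that no agreement statistic is planned, so lower agreement affects the analysis only through the averaged score. Finally, asking raters afterwards which reading they used relies on recall and gives no clean answer if they guessed case by case. None of this removes the duplicated wording; it supports a low severity.

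**Conclusion.** The concern holds, as a minor error. That the wording is wrong as printed is certain; that code 2 was meant to refer to less than half is a strong inference for the study team to confirm. One of the twelve scored items is affected, by at most 2.8% of the score range for a participant if items are summed, and more plausibly by 0.9% or nothing. Any shift in group means is a fraction of a point and depends on unequal shares of partial recoil. The figures rest on the assumed way of combining items, the assumed SDs and the assumed shares, none of which the plan gives. The error does not threaten the study's conclusions, but it is a faulty rule in the instrument that produces the dependent variable.

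**What to change.** Confirm the intended wording with the study team and, before scoring, change the word more to less in item 7, code 2, to match Appendix 4 items 1, 4 and 6 and Appendix 5. Check that the form the raters actually use carries the same correction.

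If scoring has started, ask each rater which reading was applied. If all three used less than half, correct the form and do not re-score. If any did not, or cannot say, re-score item 7 alone, blind to group. The recordings make this possible, since "All performants will be videotaped during simulation".

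Exactly 50% would still have no code, as in the six parallel items; one line in the rater instructions can settle it for all of them.

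Before scoring, the cost is a one-word edit. At worst, three raters watch the existing videotapes again for one item. The plan gives no number of mannequin participants, so total rater time cannot be stated. No new data are needed.

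### Item 9 of the CPR Evaluation Form asks whether mask ventilation was effective, but scores a failed attempt 3 of 4, above a careless one, and has no code for effective but imperfect ventilation

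*Combined protocol and SAP*

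**What the plan says.** Appendix 4 (CPR Evaluation Form) opens with "Please rate participants' CPR performance from 1 to 4 based on the questions below". The question in item 9 is "Did he/she perform effective mask ventilation", and its codes are:

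- 1: "Did not perform mask ventilation"
- 2: "Performed mask ventilation carelessly"
- 3: "Performed mask ventilation but failed"
- 4: "Completely correct one-hand mask ventilation/bedside position"

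The section Part Two: Mannequin Study says that the videos will be "evaluated and scored separately by three independent resuscitation instructor anesthesiologists who are blinded to groups". It then says: "The total simulation score will be obtained by adding the objective scores obtained from the simulator's data" to the average of the raters' scores. Under Analysis of data, the simulation score is the dependent variable of the 2x2 ANCOVA. The documents contain no rater guide and do not define careless or failed.

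**The concern.** An ordinal item is useful only if a higher code means more of what the item asks about. Here the question is about effectiveness, while the codes move from whether ventilation was attempted, to how carefully, to whether it failed, to whether hold and position were fully correct. Two performances that a rater may well meet are handled badly. A failed attempt earns the second-highest mark. An attempt that worked but was not fully correct has no code of its own.

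Nothing else in the score corrects for this. Item 5 covers the compression-to-ventilation ratio and item 8 covers pauses. The mannequin scores in Appendix 5 cover compression rate, depth and place only. Item 9 is thus the only measure of ventilation quality in the dependent variable.

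**Working it through.** The plan states no score range, sample size, standard deviation or effect size, so there is no figure of its own to reproduce. The check compares the codes with the question and then sizes the problem.

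**Codes against the question**

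| Code | What it grades | Was ventilation effective? |
|---|---|---|
| 1 | attempt | no, not performed |
| 2 | care taken | not stated |
| 3 | outcome | no, failed |
| 4 | technique and position | implied |

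Effective ventilation with imperfect technique does not meet code 4 and contradicts code 3. It fits code 2 only if the rater also regards it as careless. A rater who must choose could defend 2, 3 or 4. Item 3 of the same form asks the parallel question about compressions and grades it by share of time effective (under 25%, 25–50%, 50–75%, over 75%), so the form already contains a scale that follows effectiveness.

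**Size on the item**

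- Item spread: 4 − 1 = 3 points.
- Share of the spread kept by a failed attempt: (3 − 1)/3 = 67%.
- Reversal if careless but effective ventilation is coded 2 and failed ventilation 3: 3 − 2 = 1 point.
- Ambiguity for effective but imperfect ventilation: 4 − 2 = 2 points.

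**Size on the total**

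Inputs: 9 items in Appendix 4 and 3 in Appendix 5, each scored 1 to 4. Assumption: unweighted sums within each form; the protocol says only that the two parts are added.

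- Minimum (9 + 3) × 1 = 12; maximum (9 + 3) × 4 = 48; span 48 − 12 = 36.
- Item 9: 3/36 = 8.3% of the span.
- Reversal: 1/36 = 2.8%.
- Ambiguity: 2/36 = 5.6%.

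**Effect of averaging three raters**

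Suppose all three code a failed attempt 3. For a careless but effective performance, let k raters choose 2 and the rest choose 3. The item mean is (2k + 3(3 − k))/3.

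| k | Mean, careless but effective | Shortfall against failed (3.00) |
|---|---|---|
| 3 | 2.00 | 1.00 |
| 2 | 2.33 | 0.67 |
| 1 | 2.67 | 0.33 |
| 0 | 3.00 | 0 (tie) |

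If the raters read the codes alike at 2, averaging removes none of the reversal. If they split between 2 and 3, it removes part. If they spread over 2, 3 and 4, the mean is (2 + 3 + 4)/3 = 3.00, and effective ventilation only ties with failed ventilation.

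**The case against.** The strongest defence is that the codes grade quality of performance, which is what the form's opening line asks for: not done, then a perfunctory attempt, then a proper attempt that did not succeed, then a fully correct one. On that reading the order is monotone, and a careful failure rightly outranks a careless attempt. If careless ventilation also fails, codes 2 and 3 do not differ in effectiveness at all.

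This shows that the reversal is conditional. It does not remove the defect. The reading answers a different question from the one printed, it is not written down for the raters, and it still leaves effective but imperfect ventilation without a code. A translation slip is possible (codes 2 and 3 of item 7 are identical as printed), but the documents cannot show it, and the raters will work from the form as it stands.

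Two further objections stand in part. The raters score separately, so divergent readings are partly averaged out. And whether hold and position belong in the top code is a legitimate scoring choice, provided that effectiveness is graded somewhere.

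A reader might infer that a threat effect which makes ventilation fail would raise the score. The documents do not support that. A participant who falls from fully correct to failed moves from 4 to 3, the expected direction. An untidy participant who then fails still fits code 2. A rise needs someone who was effective but careless to become ineffective and no longer careless.

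**Conclusion.** The point holds as a mismatch between the question and the codes, with a gap in the scale. Effective but imperfect ventilation can score at or below a failed attempt. The ambiguity is up to 2 points (5.6% of a 36-point span), and the reversal is 1 point (2.8%) if careless but effective ventilation is coded 2. The percentages rest on unweighted sums.

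The documents do not show that the item always runs backwards, that code 2 is the only one open to such a performance, or how many participants would be affected. Nor do they show bias between experimental and control groups: participants are randomised within each physician group and the raters are blinded. The likely harm is measurement error and reduced validity in one of 12 items. Its effect on the ANCOVA cannot be computed without a standard deviation, effect size or sample size. The point is modest in size but worth correcting, because this is the only item on ventilation quality.

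**What to change.** Before the videos are scored, reword the item 9 codes so that they rise with effectiveness, as item 3 does for compressions. For example: 1 = not performed; 2 = performed, no breath effective; 3 = effective in some breaths; 4 = effective in all or nearly all breaths. Give the three raters a written definition of an effective breath as judged from video, for example visible chest rise. This matters because the mannequin scores include no ventilation data.

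If technique is to be kept, score it as a separate item, or add an explicit effective-but-imperfect level above failed. Either would change the score range, which should then be restated.

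The cost is four reworded lines and a short definition, with no new data or staff. Because scoring takes place later from video, the revised form can be applied to every participant. The small downside is that technique would no longer be graded within this item.

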## **APPENDIX 5: MANNEQUIN SCORES**

Scores of cardiopulmonary resuscitation simulator mannequin (Resusci Anne Simulator®, 'Laerdal Medical').

1. Chest compression number per minute (n: 100-120)
  1. Too fast or too slow
  2. In correct range less than 50% of the time
  3. In correct range more than 50% of the time
  4. In correct range all the time
  
2. Chest compression depth (n: 5-6 cm)
  1. Too deep or too superficial
  2. At the appropriate depth less than 50% of the time
  3. At the appropriate depth more than 50% of the time
  4. At the appropriate depth
  
3. Are the chest compressions applied to the correct place?
  1. Completely wrong place (ex: abdomen)
  2. Correct place - less than 50% of the time
  3. Correct place - more than 50% of the time
  4. Completely correct place
